We will meet with each adolescent online for 1 hour to collect further information using an intake assessment form (see the attached "Intake assessment form"). The form will assess headache history and coping responses. The research team will combine the information gathered in phase 1 and phase 2 to create a case conceptualisation. We will also create some brief goals for treatment and will identify key target processes (e.g., psychological coping responses, such as learning what to do during a headache episode) for the personalised intervention. We will collaboratively select 2-3 most personally relevant items from the previously completed PBAT questionnaire (in phase 1), which will form part of further data collection. These questionnaire items will be those deemed to be most relevant to the adolescents' presenting headache concerns, and these will guide the focus of the upcoming intervention. Finally, in Phase 2 we will introduce the upcoming data collection schedule which is described in Phase 3 below.

Phase 3: baseline data.

Participants will begin the Ecological Momentary Assessment (EMA), which they will complete 2-3 times per day, on 3- 4 days per week. The participants will be sent completion prompts via the mPath app. The questionnaires will take up to 2 minutes to complete each time. As per feedback from experts by experience, data collection will be distributed over several days per week to reduce participant burden (e.g., Monday, Wednesday and Friday). At this stage, participants will be completing both primary outcome measures (headache activity, progress towards the personalised goal, and coping with headache), and their personalised PBAT items. Once per week, participants will also receive a questionnaire assessing headache interference and headache-related disability.

Phase 4: intervention and further data gathering.

Each participant will be invited to attend up to 5 weekly online brief therapy sessions, lasting 30 minutes each, to work on the specific target processes identified in Phase 2. The personalised interventions will be drawn from already known evidence-based CBT-based treatments for headache

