management. Clinical supervision during this treatment phase will be provided by the lead project supervisor who holds extensive clinical and research experience in chronic headaches. Due to the intervention being highly personalised, adherence to a specific treatment protocol will not be measured. Additionally, we will administer a Client Feedback Form at the final session.

Participants will begin interventions at different time points, in line with the Multiple-Baseline SCED Design. This will mean that some participants will spend longer completing Baseline data before they begin the intervention phase. We expect the baseline period to be no longer than 2 weeks at most, ranging from several days to 2 weeks. The multiple baseline design protects validity of research by controlling for the effect of passage of time on the results (Slocum et al., 2022). We aim to randomise participants into multiple baselines, rather than selecting participants, to reduce the risk of researcher bias (Levin and Ferron, 2021).

The data collection schedule will remain the same as in Phase 3 (i.e. on 3 days per week, participants will receive 2-3 prompts to fill out a brief questionnaire, and once per week they will receive a prompt to complete a measure of headache-related disability and interference).

The personalisation will be an ongoing collaborative process. This means that the research team will revise the collected data each week, which will consequently inform each session's focus. Within PBT, the network map is viewed as always changing and therefore is revisited frequently during therapy (Ong et al. 2022). Within our study, we will use the network map as the preliminary case conceptualisation to identify key processes that might be contributing to headache-related disability. Consequently, we will collect weekly EMA data in between intervention sessions, and share this with participants to update the network diagram and to identify the key focus of the subsequent treatment sessions. The PBT network map, along with weekly intensive EMA data collection, during treatment and at follow-up, will help us to create a highly personalised, dynamic psychological intervention. The weekly EMA idiographic data will be reviewed with adolescents and will guide:

- a) Network case formulation
- a) Processes to focus on the personalised intervention
- b) Decision-making on the overall course of treatment.

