Data collection schedule: In line with recommendations arising from 24 EMA studies with adolescents, a “burst design” for data collection may be optimal to reduce participant burden (Heron et al, 2017). Participants will therefore have periods of breaks from data collection during each week. This has also been advised by EBEs who took part in trialling the data collection schedule. Compliance with questionnaire completion will also be measured.

Phase 5: Follow-up.

Following intervention completion, participants will continue completing daily questionnaires for a further 1-2 weeks, as well as weekly measures of headache-related disability and interference.

Study end. At the end of the follow-up period, participants will be contacted by email to inform them of the end of the study and to thank them for their participation. Additionally, we will offer an optional online debrief meeting to each participant.

Sample recruitment

The sample will be recruited from a specialist paediatric NHS service (initial discussions are currently ongoing). Clinical staff will identify participants by screening adolescents against the criteria and seeking verbal consent to pass their details to the research team to discuss study participation.

We aim to recruit an adolescent sample size of 12 (to allow for sample attrition) ranging in ages 12-18. We are aiming for a final sample of $n=6$ (i.e. number of participants who complete the study). This sample size is in line with other previous SCED studies with adolescents (e.g., Cawthorne et al., 2022; Sukhodolsky et al., 2013).

Table 1.

Inclusion and exclusion criteria for the study:

Inclusion	Exclusion

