1. Perceived progress in a personally defined goal (1 item)
2. Perceived progress in ability to cope with headache (1 item)
3. Headache activity (frequency, duration, intensity and interference) (4 items)

Secondary outcome measures

Participants will respond once per week in a series of standardised measures, using a total of 2 questionnaires as outlined below.

1. Headache interference. The Patient Reported Outcomes Measurement Information System (PROMIS) Paediatric Pain Interference (PPI) Item Bank- 10 items (Varni et al. 2010) measures the daily interference of pain on physical, psychological, and social functioning. Higher scores indicate greater pain interference in the child's life. This is a unidimensional item bank (Varni et al., 2010), derived from a larger PROMIS item bank which has an overall good internal consistency (Cronbach's alpha= 0.98) (Cunningham et al. 2017) and convergent validity shown by significant correlations with other similar scales. The PPI scale has been validated in paediatric chronic pain samples (Ceniza-Bordallo et al., 2022).

2. Measure of headache-related disability. Headache-related disability will be measured using the Paediatric Migraine Disability Assessment Scale (PedMIDAS) (Hershey et al. 2001), which is a 6-item

questionnaire measuring the frequency of disruption to daily activities caused by headaches. This measure has been used in studies measuring headache related disability after pharmacological interventions (Powers et al., 2021). The PedMIDAS has been shown to have internal consistency (Cronbach's alpha 0.80) and validity in measuring headache-related disability (Hershey et al. 2001).

Other measures

Additionally, we will administer a Client Feedback Form at the final intervention session, based on Sekhon et al.'s (2018) theoretical framework of acceptability (TFA) for health interventions. This includes six items, rated on a 5-point Likert scale: affective attitude, burden, perceived effectiveness, intervention coherence, self-efficacy, and opportunity/ costs.

Statistical analyses

To address the first research question, we will analyse the weekly standardised data to assess change in disability (PedMIDAS) and headache interference (PROMIS) assessing reliable change (RC) and clinically significant change (CSC), using Jacobsen & Traux's formula (1991). (Scores will be compared against a calculated reliable change index, to indicate whether the level of change is statistically significant).

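### Acceptability is rated only at the final therapy session, so participants who stop therapy unplanned are not asked and the rating is at risk of selection bias, probably upward

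*Protocol*

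**What the plan says.** The Client Feedback Form appears in two places, and both give the same single time point. Phase 4 of the Protocol says "we will administer a Client Feedback Form at the final session". The Other measures section says "we will administer a Client Feedback Form at the final intervention session" and lists six items on a 5-point scale: affective attitude, burden, perceived effectiveness, intervention coherence, self-efficacy and opportunity/costs. No other acceptability rating is described.

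The number of sessions is not fixed: "Each participant will be invited to attend up to 5 weekly online brief therapy sessions" (Phase 4).

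Sample recruitment sets a target of 12 recruits as an allowance for attrition and a final sample of 6, defined as the "number of participants who complete the study". No dropout rate is stated.

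The Informed Consent section lets participants withdraw at any time without giving a reason and keeps the data collected up to then. It describes no exit questionnaire. The Study end paragraph offers an optional debrief, which is not described as collecting ratings. Questionnaire compliance is also measured, but that is not a rating of the therapy.

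**The concern.** A form tied to the final session reaches only those who get there. Several of its items, notably burden, affective attitude and perceived effectiveness, are plausible reasons for leaving. Whether a rating is obtained may therefore depend on what the rating would have been.

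The protocol treats burden as a real issue: it spreads prompts over several days and adopts a burst design to limit it. It also plans for the loss of up to half its recruits. Under that plan, a favourable mean could come entirely from those who stayed, with nothing recorded from those who gave up the therapy part-way. An analysis plan cannot repair this afterwards, because ratings that were never requested cannot be recovered.

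What is at stake is how the acceptability result is read, and what a later study would take from it. The efficacy and process results do not depend on this form.

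**Working it through.** **Inputs from the Protocol.** Recruits: 12. Study completers aimed for: 6 (both from Sample recruitment). Form: once, at the final session (Phase 4 and Other measures). Scale: 1 to 5.

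**Step 1: the attrition allowance.** Implied allowance = 1 − 6/12 = 50%, and 6/(1 − 0.5) = 12, which matches the stated target. This shows only that the figures are consistent, since the 50% is derived from the same two numbers. The sample size is justified by precedent, so there is no power calculation to reproduce.

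**Step 2: who goes unasked.** Split the 6 allowed losses into *a* (before session 1), *b* (unplanned stop between the first and last session) and *c* (during follow-up), with a + b + c = 6.

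- Group *a* has had no therapy session to rate.
- Group *c* has already been given the form.
- Only group *b* has started therapy and is not asked.

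The unasked fraction of those who start therapy is b/(12 − a).

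- All losses in *b* (a = 0, b = 6, c = 0): 6/12 = 50%, the maximum under the allowance.
- Losses spread evenly (a = b = c = 2): 2/10 = 20%.
- No losses in *b*: 0%.

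The protocol does not say how losses are expected to divide.

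**Step 3: bias in the mean rating.** Let n start therapy and m go unasked, with mean A among those asked and mean U among those not asked. Then

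bias = A − [((n − m)/n) × A + (m/n) × U] = (m/n) × (A − U).

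The gap A − U is an assumption, because the protocol gives no figure for it. With n = 12, and assuming that everyone asked replies:

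| Unasked m | gap 0 | gap 0.5 | gap 1 | gap 2 |
|---|---|---|---|---|
| 2 of 12 | 0 | 0.08 | 0.17 | 0.33 |
| 4 of 12 | 0 | 0.17 | 0.33 | 0.67 |
| 6 of 12 | 0 | 0.25 | 0.50 | 1.00 |

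**Step 4: the sign.** Take an assumed mean of 4.0 among those asked and the maximum of 6 unasked. The mean over all 12 would be 2.5 if leavers would rate 1, 3.5 if they would rate 3, 4.0 if they would rate 4, and 4.5 if they would rate 5. The reported 4.0 would be too high in the first two cases, correct in the third and too low in the last. The sign depends on ratings that the plan does not collect.

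**The case against.** The strongest reply is that acceptability is not an aim of this study. The stated focus is pilot efficacy and process of change, neither research question mentions acceptability, and the form is listed under Other measures with no threshold or success criterion. This stands, and it sets the weight of the point: no primary or secondary result is affected.

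A reader might go further than the documents allow in three ways.

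- **That half the sample is expected to leave unasked.** The protocol makes an allowance and gives no expected rate. The 6 counts people who finish the whole study, including follow-up, so some losses may fall after the form or before any therapy.
- **That the rating is biased upward as a matter of fact.** No reasons for leaving and no leaver ratings are given. Participants may leave because of school commitments, prompt load, illness or improvement. Upward is the likely direction but has not been shown.
- **That the treating researcher collects the form in the session and so invites favourable answers.** The protocol says when the form is given. It does not say by whom, in what mode, or whether the therapist is present. The Confidentiality section says outcome measures are collected through mPath and Qualtrics, which may or may not cover this form.

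Two further replies have some force. Because the number of sessions is a maximum, an agreed early finish could still include the form, so only an unplanned stop misses it. And since withdrawal needs no justification, any form at exit must be voluntary, so some selection will remain. Neither reply supplies a rating from a participant who simply stops attending.

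**Conclusion.** The point holds as a minor one. As written, the plan obtains acceptability ratings only from those who reach a final session, and nothing else in the protocol fills the gap for those who stop unplanned after starting. The reported mean is therefore at risk of selection bias, probably upward.

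If all 12 start therapy and the gap in means lies between 0 and 2 points, the overstatement runs from 0 to 0.33 points with 2 unasked and from 0 to 1.0 with 6 unasked. The last figure combines the maximum loss under the allowance with the largest gap considered, so it is a limit and not a forecast. If leavers would have rated the therapy higher than stayers, the bias would run the other way.

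**What to change.** Send the same six-item form by Qualtrics link, to be completed outside the session, after each participant's last attended session. That may be the planned final session or the point of withdrawal. Make it optional at withdrawal, in keeping with the right to leave without justification.

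Report therapy completers and early leavers separately, each with the number who answered out of those who started therapy. Limit any statement about acceptability to those who responded.

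The cost is small: Qualtrics is already in use, so the change needs one extra link and a line in the information sheet. If every participant who started therapy replied, the non-response bias would be zero. In practice some who withdraw will not answer, so some selection will remain, but the stated denominator will make it visible.

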A distinct aspect of PBT intervention is ongoing data collection, using methods such as Ecological Momentary Assessment (EMA). Using EMA, we will repeatedly sample symptoms, coping with headache responses, and relevant pain-related behaviours. EMA collects data that captures frequent momentary information from adolescents in the context of their lives, longitudinally (Hedeker et al., 2012). It also helps adolescents increase self-awareness, insight, and self-management of their

headache difficulties (Folkersma et al. 2021). In this study, we will use EMA to collect weekly data, which will inform progress tracking and allow personalised treatment trajectory.

Aim of the project and research question

The objective of this project is to construct idiographic case conceptualisations and deliver brief personalised interventions, guided by weekly data that will inform the course of the intervention. This study will focus on both the pilot efficacy and process of change examination of a highly personalised intervention, collecting baseline, weekly, post-intervention and follow-up data.

Our research questions are:

(a) Is a highly personalised intervention with weekly feedback provision effective in lowering headache disability and improving headache interference?

(b) Does a personalised intervention lead to changes in clinically targeted psychological processes, personalised goals and headache activity (outcomes)?

Plan of investigation

Design

This is a single-case experimental design (SCED) study, with concurrent multiple baselines within-subjects. We will use an AB design, where baseline (A) will always precede the intervention (B) phase for each participant. This design allows participants to act as their own control (Krasny-Pacini & Evans, 2018), whilst also maintaining experimental control. We will follow the SCRIBE statement (Tate et al., 2016) to guide the reporting of this SCED design.

Each participant will partake in a baseline data collection, between 1 to 2 weeks before we deliver the intervention. Participants will not be able to begin any psychological intervention for headaches during the study. Below, we present all the phases of the study.

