To address the second research question, we will examine change in personalised goal, headache activity (VAS items), and personalised processes of change (BPAT) across time. The longitudinal data will be plotted on a line graph to allow a visual analysis for patterns, trends and variability in the data (Dowdy et al., 2022). We will supplement the visual analyses with Tau-U statistical analyses to assess the proportion of overlap between phases.

We will additionally follow a tutorial by McDonald (2022) to conduct individual dynamic regression analyses using a time-lag model, using SPSS. We will develop models, based on periods of feedback provision (one per week- overall 5 tested models). For these analyses we will estimate the

autocorrelations with lag numbers representing previous data points (e.g., data from sessions 1-5 will be included). The lagged idiographic outcome variables (headache interference and activity) will be entered into the regression model along with predictor(s) (the BPAT items) to identify whether a significant relationship exists between the predictor and the outcome, while accounting for any autocorrelation.

Ethical considerations

This study will require ethical approval from the RHUL Ethics Committee and the NHS Research Ethics Committee. Research guidelines and principles of the BPS Code of Ethics and Conduct will be followed throughout the project. Several ethical issues arising from this research are detailed below:

Informed Consent

Informed consent will be sought from both the participant and their primary caregiver or parent. Consent will be obtained electronically and, and electronic signed copies of consent forms will be stored in a RHUL's databases, accessible only to the research team. Appropriate time will be given during enrolment to ensure that participants fully understand the purpose of the study and study requirements. Participants and their caregivers will be provided with an e-copy of the information sheet.

Participants and their caregivers will be made aware that their involvement with the study is fully voluntary and that they are able to withdraw from the study at any point without justification, which will not impact their reimbursement for participating. Participants will also be made aware that any data collected up until the point of withdrawal will be anonymised and retained for analysis, to protect the validity of the study.

HeadFlex study

Project proposal, Royal Holloway University of London V3

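### Coping is a primary outcome with no named analysis, and the effectiveness question rests on secondary weekly scores analysed without the A-B contrast

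*Protocol*

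**What the plan says.** **Primary outcomes.** Under Primary outcome measures the protocol lists three, all on 0-100 visual analogue scales: "Perceived progress in a personally defined goal (1 item", "Perceived progress in ability to cope with headache (1 item" and "Headache activity (frequency, duration, intensity and interference) (4 items". That is 1 + 1 + 4 = 6 items. Phase 3 repeats the set: "primary outcome measures (headache activity, progress towards the personalised goal, and coping with headache".

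**Research questions.** Question (a) asks whether the intervention is "effective in lowering headache disability and improving headache interference". Question (b) asks about "changes in clinically targeted psychological processes, personalised goals and headache activity (outcomes".

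**Analysis for (a).** Statistical analyses states that "we will analyse the weekly standardised data to assess change in disability (PedMIDAS) and headache interference (PROMIS) assessing reliable change (RC" and clinically significant change. Both scales are listed under Secondary outcome measures and are completed once a week.

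**Analysis for (b).** The next paragraph states that "we will examine change in personalised goal, headache activity (VAS items), and personalised processes of change (BPAT) across time", using line graphs, visual analysis and Tau-U for overlap between phases. (BPAT is taken here to be the PBAT named elsewhere.) The dynamic regression has headache interference and activity as its outcomes and the PBAT items as predictors.

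**Design.** Each participant has a baseline phase A followed by an intervention phase B. Start points are staggered, and the protocol aims to assign them at random. Phase 4 relies on this stagger to guard against change that time alone would bring.

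**The concern.** There are two gaps, both in the current text.

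First, coping has primary status in two places, yet the section that assigns outcomes to analyses leaves it out. The team would then have to decide how to analyse a primary outcome after seeing the data, or could leave it aside.

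Second, the design's protection against change over time comes from comparing phases across staggered starts. The only question worded in terms of effectiveness is given an analysis that does not use that comparison. Recurrent headache can ease for reasons unrelated to treatment, and reliable change on a weekly scale would count such easing as improvement. An answer of yes to question (a) would then not have the support that the design was chosen to give.

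**Working it through.** The protocol states no alpha, power or effect size on this point, so it has no figure to reproduce. The check maps outcomes to questions and analyses, then counts observations to see which remedy is feasible.

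**1. Mapping**

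| Outcome | Status | Question | Stated analysis |
|---|---|---|---|
| Personal goal (1 VAS item) | Primary | (b) | Visual, Tau-U |
| Coping (1 VAS item) | Primary | Not named as an outcome | None named |
| Headache activity (4 VAS items, one of them interference) | Primary | (b) | Visual, Tau-U, dynamic regression |
| Selected PBAT items | Process | (b) | Visual, Tau-U; regression predictors |
| PedMIDAS | Secondary | (a), disability | Reliable and clinically significant change |
| PROMIS pain interference | Secondary | (a), interference | Reliable and clinically significant change |

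So 2 of 3 primary outcomes (1 + 4 = 5 of 6 items) have a question and an analysis. Coping, 1 of 3 outcomes and 1 of 6 items, has none.

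**2. What reliable change can show.** The index divides the difference between two scores by the spread expected from measurement error. Its inputs are the two scores and the scale's error. The length of the baseline and the date the intervention began do not enter. It can show that a score moved by more than measurement error, but not why. The protocol also does not say which weekly scores are to be compared.

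**3. Would an overlap test on the weekly scores repair (a)?** Phase 4 puts the baseline at several days to 2 weeks, which gives about 0 to 2 weekly scores. (The Design section says 1 to 2 weeks, which gives 1 or 2.) Up to five weekly sessions give about 5 scores, and follow-up adds 1 or 2. If scores are treated as exchangeable, which is an assumption, complete separation of the phases gives the smallest possible one-sided p of 1/C(nA + nB, nA). The two-sided value is twice that.

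- 1 v 5: C(6,1) = 6; one-sided 1/6 = 0.167, two-sided 0.333.
- 2 v 5: C(7,2) = 21; one-sided 1/21 = 0.048, two-sided 0.095.
- 2 v 7 (two follow-up scores counted with B): C(9,2) = 36; one-sided 1/36 = 0.028, two-sided 0.056.

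Even perfect separation does not reach a two-sided 0.05 in any one participant. That threshold is a yardstick used here, not one the protocol sets.

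**4. Is a phase comparison feasible for the VAS items?** Phase 3 gives 2 to 3 prompts a day on 3 to 4 days a week: 2 × 3 = 6 to 3 × 4 = 12 prompts per baseline week. Phase 4 describes 3 days a week: 2 × 3 × 5 = 30 to 3 × 3 × 5 = 45 prompts over five weeks. These counts assume that every prompt is answered and all five sessions take place; a baseline of only several days gives fewer. Within those limits the comparison is feasible for coping and for interference.

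**The case against.** The strongest reply is that little is missing. The personal goal and all four headache-activity items match question (b) and its analysis. The interference item already gets its visual and Tau-U phase comparison there, so for interference the issue is where the result is reported. Coping may be meant to fall under the targeted processes of question (b), since Phase 2 gives coping responses as an example of a process. A sentence that lists outcomes might also be completed in an analysis plan that is not shown.

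The first two points stand and limit the concern. The third does not close the gap: the analysis measures processes through the PBAT items, and the coping VAS item is separate from these. The tag for VAS items follows headache activity and does not clearly extend to coping. The fourth is possible, but this section does assign outcomes to analyses, and it leaves a primary one out.

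A reader might infer more than the text supports:

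- *That the weekly scales lie outside the A-B design.* They do not. They are collected in baseline, intervention and follow-up (Phases 3 to 5). Only the planned analysis ignores the phases.
- *That coping will go unreported.* The protocol says the longitudinal data will be plotted and does not exclude coping. What is missing is a named analysis.
- *That six co-equal primary items carry a calculable false-positive rate.* The protocol sets no significance level for these items and uses Tau-U to supplement visual analysis. Four of the items rate the same headaches, so independence is implausible. No such figure can be drawn from the document.
- *That one primary outcome must be chosen.* Making the interference item the sole primary outcome would leave the disability half of question (a) unanswered and would demote the personal goal in an idiographic study.

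**Conclusion.** The concern holds in this limited form. One of three primary outcomes (1 of 6 VAS items) is named in no analysis. The effectiveness question is answered only by two secondary scales, through a method that uses neither the phase contrast nor the staggered baselines and so cannot separate an intervention effect from change over time. For interference, the better-controlled comparison is already planned under (b) but is not brought to (a). For disability, no VAS item exists, and the sparse weekly baseline means its evidence can only be descriptive.

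This rests on reading the list under question (b) as complete, and on reliable and clinically significant change being the whole analysis for (a), as written. The p-value floors assume exchangeable weekly scores and serve only to show that adding Tau-U to those scales would not be a remedy. The matter should be corrected before analysis.

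**What to change.** Change the Statistical analyses section in three places.

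1. In the paragraph on question (b), add the coping VAS item to the outcomes compared between phases by visual analysis and Tau-U.
2. In the paragraph on question (a), name the A-B comparison of the headache-interference VAS item as the design-controlled evidence for the interference half. Say that it is read across participants against their staggered start points, because Tau-U within one participant does not by itself use the stagger.
3. In the same paragraph, state that the PedMIDAS and PROMIS reliable and clinically significant change results are secondary and descriptive, and that disability has only this descriptive evidence.

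The cost is protocol wording. All the data are already to be collected, and the interference comparison is already planned; coping adds one item to an existing analysis. The downside is a slightly more modest claim for question (a), mainly on disability.

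### Fitted week by week, the five individual dynamic regressions have only 0 to 4 residual degrees of freedom at three prompt days, too few for an informative test of process against outcome

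*Protocol*

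**What the plan says.** Under Statistical analyses, after the graphs and Tau-U, the Protocol adds a plan "to conduct individual dynamic regression analyses using a time-lag model, using SPSS". On the number of models it says "We will develop models, based on periods of feedback provision (one per week- overall 5 tested models"). On their content: "The lagged idiographic outcome variables (headache interference and activity) will be entered into the regression model along with predictor(s) (the BPAT items"). The stated purpose is to find a significant relation between predictor and outcome while allowing for autocorrelation. Lags are described as standing for previous data points, and an example in brackets says that data from sessions 1 to 5 are included.

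The inputs stand elsewhere in the Protocol:

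- Phase 2, number of items: "We will collaboratively select 2-3 most personally relevant items from the previously completed PBAT questionnaire".
- Phase 3, EMA schedule: "which they will complete 2-3 times per day, on 3- 4 days per week".
- Phase 4 says the schedule is unchanged from Phase 3, but describes it as "on 3 days per week, participants will receive 2-3 prompts to fill out a brief questionnaire".
- Phase 4, sessions: "Each participant will be invited to attend up to 5 weekly online brief therapy sessions, lasting 30 minutes each".
- Data collection schedule, burst design: "Participants will therefore have periods of breaks from data collection during each week".

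**The concern.** The models are individual, so nothing is borrowed across participants. If each one also uses a single week, a handful of records must support nearly as many coefficients. A non-significant week then says almost nothing, and a significant one needs a near-perfect partial correlation. At the low end of the schedule there is no test at all.

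The lag adds a second problem. Prompts come in bursts on separated days (Phase 3 gives Monday, Wednesday and Friday as an example). The previous data point is therefore sometimes a few hours back and sometimes days back, and one lag coefficient cannot describe both.

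At stake is the examination of processes of change, which the aims name as a focus alongside pilot efficacy. Graphs and Tau-U describe change between phases. Only these regressions relate a process to an outcome.

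**Working it through.** **The plan's own figure.** 5 weekly sessions x 1 feedback period a week = 5 models, as stated. The Protocol gives no number of observations per model and no power figure for them, so nothing else can be reproduced.

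**Inputs.** Prompts per week: 3 x 2 = 6 to 3 x 3 = 9 (Phase 4), or up to 4 x 3 = 12 (Phase 3). Coefficients: intercept + lagged outcome + 2 or 3 items = 4 or 5. Assumptions not in the Protocol: two-sided 5% level, true partial correlation r = 0.5 and, unless stated, full compliance.

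**Formulas.** Residual df = prompts - 1 (lost to the lag) - coefficients. Critical |partial r| = t / sqrt(t² + df), with t the 97.5% point of the t distribution. Power comes from the noncentral t with noncentrality r / sqrt(1 - r²) x sqrt(df + 1).

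**One week per model.**

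| Prompts | Coefficients | Residual df | Critical partial r | Power at r = 0.5 |
|---|---|---|---|---|
| 6 | 5 | 6-1-5 = 0 | no test | no test |
| 6 | 4 | 6-1-4 = 1 | 0.997 | 7% |
| 9 | 5 | 9-1-5 = 3 | 0.88 | 13% |
| 9 | 4 | 9-1-4 = 4 | 0.81 | 17% |
| 12 | 5 | 12-1-5 = 6 | 0.71 | 25% |
| 12 | 4 | 12-1-4 = 7 | 0.67 | 29% |

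Example at 4 df: t = 2.776, and 2.776 / sqrt(7.71 + 4) = 0.81. A simulation with autocorrelated outcomes agrees: power 6% (6 prompts, 2 items), 17% (9 prompts, 2 items) and 12% (9 prompts, 3 items), with a false-positive rate near 5% in each.

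**Kinder readings, 6-9 prompts.** If the lag carries over from the previous week, one row is regained: 1-5 df, power at most 21%. If items enter one at a time (3 coefficients, one row lost): 2 df at 6 prompts and 5 at 9, power 10% and 21%.

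**Missed prompts.** The Protocol gives no expected compliance. At an assumed 70-80%, average df = prompts x compliance - 1 - coefficients. That is -1.8 to -0.2 at 6 prompts and 0.3 to 2.2 at 9, before counting rows whose lag is missing.

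**Accumulating weeks.** Week 1 keeps 0-4 df. Week 2 has 12-1-5 = 6 to 18-1-4 = 13 df (power 25-52%). Week 5 has 30-45 prompts and 30-1-5 = 24 to 45-1-4 = 40 df. Its critical partial r is 0.39 to 0.30, with power 79-95% at r = 0.5 and 33-50% at r = 0.3. Each model contains the data of those before it, so the five are not separate tests.

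**Lag spacing.** At 2 prompts a day a week has 6 - 1 = 5 consecutive pairs. Three lie within a day and 2 cross days, so 2 of 5 lags span a multi-day gap. At 3 prompts a day it is 2 of 8.

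**The case against.** The strongest reply is that these regressions are an addition. Research question (b) asks whether processes, goals and headache activity change, and the Protocol answers that first with visual analysis and Tau-U. This stands: a reader might infer that question (b) rests on the regressions, and it does not.

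Secondly, the bracketed example about sessions 1 to 5 allows accumulated or pooled data. This also stands, so the week-by-week figures are conditional. It does not rescue a plan for five models, because the first stays as thin and the rest overlap. Nor do a fourth prompt day or single-item entry remove the problem, as shown above.

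Thirdly, details of lag order and missing prompts may sit in an analysis plan that is not shown. That is fair for the details. But the Protocol itself fixes the number of models and describes the lag as the previous data point.

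Four stronger inferences are not supported:

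- That the models cannot test anything. This is true only at 0 df or below. At 3-4 df the test is valid but detects only very strong relations.
- That any missed prompt exhausts the degrees of freedom. At 9 prompts one missed in mid-week costs at most two of the 8 rows, leaving 6-5 = 1 or 6-4 = 2 df.
- That a predictable number of false positives follows. A saturated model yields no p-value, and such a count needs every model to be estimable and every null true.
- That the plan wrongly claims direction of effect. It claims only a significant relationship.

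**Conclusion.** The concern holds in conditional form. On the natural week-by-week reading, three prompt days leave 0-4 residual df per model with one row lost to the lag. The critical partial correlation is 0.81 or more where a test exists, and power is at most about 17% at r = 0.5. Twelve prompts raise this only to 6-7 df and 25-29%. Under accumulation the defect is confined to the early models, but the five then re-use the same data. The uneven lag remains under either reading unless the model allows for it.

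The prompt counts, item numbers and model count come from the Protocol. The significance level, effect size and compliance are assumptions, and compliance below 100% makes matters worse. The loss falls on the one planned link between processes and outcomes, not on the assessment of change.

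**What to change.** Replace the five weekly models with one model per participant, for one EMA outcome named in advance, over all EMA weeks. Include the lagged outcome and the personalised PBAT items, and add a phase term if baseline and follow-up records enter. The five intervention weeks alone give 30-45 prompts and 24-40 residual df at full compliance.

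Handle the uneven gaps with a continuous-time autoregressive error, or form lags within a day only. The second costs rows: over five weeks at 3 days, 5 x 3 x 1 = 15 rows at 2 prompts a day or 5 x 3 x 2 = 30 at 3. That leaves 15-5 = 10 to 30-4 = 26 df.

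State which weeks and how many items enter the model. Reconcile the 3 prompt days in Phase 4 with the 3-4 in Phase 3. Keep the weekly feedback to participants graphical.

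The cost is a change of analysis wording, with no change to planned data collection beyond settling the number of prompt days. The downside is that there are no week-specific coefficients, which these data cannot support.
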